#### **11.1.5. Pharmacokinetic Analysis Set**

The PK Analysis Set will include all subjects in the Enrolled Analysis Set who received at least 1 dose of DS-3201b and had sufficient plasma concentration data to characterize DS-3201a PK.

#### **11.1.6. Pharmacodynamic Biomarker Analysis Set**

The PDy Biomarker Analysis Set will include all subjects in the Enrolled Analysis Set who received any amount of DS-3201b and who had the mandatory baseline assessment and, where applicable, at least 1 post-baseline assessment for biomarkers.

## **11.2. General Statistical Considerations**

The primary analysis is to assess the safety and tolerability of DS-3201b in subjects with relapsed or refractory AML or ALL and to determine the RDE or establish the safety and tolerability of DS-3201b at the RDE.

The primary analysis will occur after all subjects in Part 2 have either discontinued the study or have completed at least 6 months of treatment. After the primary analysis, the main study will be closed. Subjects in Part 1 and Part 2 who are still on study at least 6 months after enrollment

of the last subject in the study may be eligible to continue receiving study drug in a separate extension phase of the protocol (see Section 17.9). Data collected from those subjects may be captured in a separate database.

Descriptive statistics will be provided for selected demographic, safety, efficacy, and PK parameters as well as plasma DS-3201a concentrations, and will be summarized by dose level/study day/time points, as appropriate. Descriptive statistics on continuous variables will include means, medians, standard deviations, minimum, and maximum (as well as geometric means and geometric coefficient of variation for Cmax and AUC PK parameters), while categorical data will be summarized using frequency counts and percentages. Graphical summaries of the data may be presented.

The last non-missing value of a variable taken before the first dose of study drug will be used as the baseline value, unless otherwise specified. Assessments of change from baseline to post-treatment or the ratio of post-treatment to baseline will include only those subjects with both baseline and post-treatment measurements. In general, missing or dropout data will not be imputed for the purpose of data analysis, unless otherwise specified.

Safety analyses will be performed based on the Safety Analysis Set. Analysis of PK parameters will be based on the PK Analysis Set and biomarker analyses will be based on the PDy Biomarker Analysis Set. Efficacy endpoints will be analyzed based on the Full Analysis Set. Data from the Dose Escalation part will be summarized by dose level and overall.

A detailed SAP describing the methodology to be used in the final analysis will be prepared and finalized before database lock. Statistical methods described within this document may be changed based on advances in research.

### **11.3. Study Population Data**

Disposition and reasons for ending the treatment and discontinuing from the study will be summarized and listed for subjects in the Enrolled Analysis Set.

Demographic and baseline characteristics such as age, sex, race, baseline ECOG-PS, organ dysfunction, histology, cancer stage, cytogenetics, de novo versus therapy-related status, molecular mutations (if available), prior stem cell transplant status, best response to prior chemotherapy, lines of prior regimens, and prior treatment regimens will be summarized for the Enrolled Analysis Set, Full Analysis Set, and Safety Analysis Set. If 2 analysis sets within a part of the study are identical to each other, the table will be presented only once.

Study drug exposure, treatment duration, and compliance with study therapy will be summarized using descriptive statistics for the Safety Analysis Set.

### **11.4. Efficacy Analyses**

Response to treatment will be evaluated using the revised IWG response criteria for AML or the NCCN response criteria 2016 for ALL, respectively (Section 17.3). The efficacy endpoints will

be CRc rate (including CR, CRi, and CRp), MLFS, PR rate, ORR, DOR, OS, and 30- and 60-day mortality rate for AML and ALL, respectively.

For the binary efficacy endpoints, the point estimate and exact 95% confidence interval will be provided. Time-to-event variables, such as DOR and OS, will be analyzed using the Kaplan-Meier method by dose level and overall.

The best overall response will be determined for each subject, in the order of CR, CRp or CRi, PR, and treatment failure (TF). For each category as well as response (CRc or PR), the point estimate and 95% confidence interval will be calculated for the proportion.

OS is the time from the first dose of DS-3201b to the death. The censoring rules will be specified in the SAP.

## **11.5. Pharmacokinetic/Pharmacodynamic Analyses**

### **11.5.1. Pharmacokinetic Analyses**

Plasma concentrations for DS-3201a will be listed, plotted, and summarized using descriptive statistics by dose level/study day at each time point. Pharmacokinetic parameters will be listed and summarized using descriptive statistics by dose level/study day.

A concentration-QTc analysis will be done using pooled data from all subjects.

### **11.5.2. Pharmacodynamic/Biomarker/Exploratory Analyses**

Descriptive statistics will be used to summarize the reported values and changes from baseline of the biomarkers by dose level and by scheduled measurement. They include:

#### Exploratory Biomarkers

- Molecular testing in blood cells and/or bone marrow cells
- Cytogenetic and molecular subsets of AML and ALL

#### Pharmacodynamic Biomarkers

- Leukemic stem cells in pre- and post-dose bone marrow cells
- H3K27me3 status in leukemic stem cells in bone marrow and/or blood cells

## **11.6. Safety Analyses**

Safety parameters will include AEs, SAEs, TEAEs, DLTs, physical examination findings (including ECOG-PS), vital sign measurements, standard clinical laboratory parameters, histamine level in plasma, and ECG parameters.

Frequency tables of subjects reporting TEAEs will be provided by the worst NCI-CTCAE grade, SOC, preferred term (PT), and by dose level. Similarly, the number and percentage of subjects reporting treatment-emergent SAEs will be tabulated, as well as treatment-related TEAEs. The incidence of DLTs will be tabulated by dose level. Descriptive statistics by dose level will be provided on clinical laboratory parameters, histamine level in plasma, ECG parameters, and vital sign measurements, including the reported values and changes from baseline at each scheduled

measurement. Frequency tables by dose level will be provided for physical examination and ECOG-PS, and other categorical assessments as appropriate.

Adverse events will be graded according to the NCI-CTCAE. In the Dose Escalation part, the incidence of DLTs will also be evaluated.

Safety analyses in general will be descriptive and will be presented in tabular format with the appropriate summary statistics. In the Dose Escalation part, the number of DLTs identified among the DLT-evaluable subjects in the DLT-evaluable Set will be listed and summarized for each dose of DS-3201b.

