##### **2.1.1.2. Part 2 (Dose Expansion)**

The primary objective of Part 2 is as follows:

1. To confirm the safety and tolerability of DS-3201b at the RDE in subjects with relapsed/refractory AML and ALL.

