### **3.1.2.2. Part 2 (Dose Expansion)**

Upon completion of Part 1 with the established MTD, RDE, and drug administration schedule, the Dose Expansion part will begin with the intention of confirming the safety and tolerability of DS-3201b and evaluating preliminary efficacy of DS-3201b in 2 separate cohorts of subjects with relapsed or refractory AML and ALL.

Four subjects with AML and 4 subjects with ALL will initially be treated to further assess safety before enrolling the remaining subjects in the respective cohorts of AML and ALL. Following completion of the Cycle 1 safety evaluation in all 4 subjects in the cohort, a safety analysis will be conducted to allow the reevaluation of the appropriateness of the dosing level. If the incidence of DLT has exceeded the EWOC principle guideline, no further treatment at the MTD and RDE level established in Part 1 will be done and dose de-escalation will be considered. Approximately 20 subjects each with AML and ALL will be enrolled in Part 2 to obtain a sufficient number of subjects treated at the RDE in these indications.

Pre-treatment bone marrow biopsies/aspirates will be required for participation in the study and optional post-treatment bone marrow biopsies/aspirates may be collected within 30 days following the last dose of study drug treatment.

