### **3.1.8. Maximum Tolerated Dose and Recommended Dose for Expansion Definition**

Once the stopping criteria are met, the MTD estimated by BLRM + EWOC is the dose with the highest posterior probability of the DLT rate in the target DLT rate interval of [16%, 33%] among all doses fulfilling the following 2 constraints:

- The overdose control constraint: There is less than a 25% probability for the DLT rate  $>33\%$  (probability for excessive or unacceptable toxicity) (Section 3.1.2.1);
- The mean of the posterior distribution of DLT target rate at this dose is  $\leq 25\%$ .

Since an alternative drug administration schedule may be explored in lieu of or in parallel with the original QD  $\times$  28/28 days schedule, separate MTDs may be identified for each regimen. The final MTD for each dosing schedule will be decided based on considerations of the respective MTDs estimated by the BLRM and on an overall assessment of safety data from subsequent cycles and PK/PDy response information collected at all different doses tested. Upon determining the final MTD of the original QD  $\times$  28/28 days and/or alternative dosing schedules, 1 dosing regimen will be selected for further evaluation in Part 2 (Dose Expansion). This regimen given at the final MTD determined in Part 1 is referred to as the “Tentative Recommended Dose for Expansion”.

In the Dose Expansion cohort, the safety will be assessed continuously after 4 subjects are enrolled in each cohort of AML and ALL. The study will be stopped if the cumulative incidence of clinically relevant  $\geq$ Grade 3 toxicities exceed 30%. The exceptions are:

- Grade 3 and higher nausea, vomiting, or diarrhea that do not require hospitalization or TPN support and can be managed with supportive care to  $\leq$ Grade 2 within 48 hours.

- Alopecia and study drug-related fever.
- Grade 3 or 4 electrolyte abnormalities that are corrected to  $\leq$ Grade 2 within 24 hours.
- Grade 3 or 4 differentiation syndrome which improves to  $\leq$  Grade 1 within 7 days of the start date of  $\geq$  Grade 3 differentiation syndrome and which is not associated with end-organ damage.

Evaluation of myelosuppression will be decided between the Investigators and Sponsor Medical Monitor during safety review meetings.

In the Dose Expansion cohort, the efficacy will be assessed continuously after 10 subjects are enrolled. The study will be stopped if the cumulative ORR will be less than 10%.

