## **9.3. Adverse Events of Special Interest**

Differentiation syndrome is an adverse event of special interest (AESI) for DS3201-A-U102 and as of 18 Jan 2020, it has been reported in 1 subject with AML.

When subjects with acute leukemia are treated with DS-3201b, vigilance should be exercised in while monitoring them for development of possible differentiation syndrome. It is important to both promptly recognize the signs and symptoms of differentiation syndrome and implement prompt management.

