#### **11.1.2. Safety Analysis Set**

The Safety Analysis Set will include all subjects enrolled who received any amount of DS-3201b. Subjects will be summarized according to dose of DS-3201b received.

Four groups of subjects will be identified within the Safety Analysis Set: (1) subjects in the Dose Escalation part, (2) subjects in the Dose Expansion part, (3) subjects treated at the dose level of RDE, and (4) all subjects in the study.

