## 11.10. Sample Size Determination

The Dose Escalation part of the study will enroll 3 to 6 subjects in each cohort, based on a BLRM under the EWOC principle. It is possible that a dose level may enroll more than one cohort based on the BLRM recommendation. The number of subjects enrolled depends on the observed DLTs, but it is expected that 21 or more subjects might be enrolled in the Dose Escalation part.

For the Dose Expansion part, additional subjects will be enrolled at the RDE dose level as suggested based on data in the Dose Escalation part. Approximately 20 subjects each with AML and ALL will be enrolled at the RDE dose level, including those dosed at the same dose level in the Dose Escalation part, which is expected to number between 6 and 9. The size of 40 is deemed to be sufficient for the assessment of safety and tolerability, as well as the clinical antitumor activity. Assuming a true CRc rate of 20%, the probability of observing 3 or more CRc among the 20 subjects is 79.4% for AML and ALL, respectively.

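### The planned safety tables have no AML/ALL split, although safety at the RDE in both diseases is the primary objective of Part 2

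*Combined protocol and SAP*

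**What the plan says.** Section 2.1.1.2 gives Part 2 one primary objective: "To confirm the safety and tolerability of DS-3201b at the RDE in subjects with relapsed/refractory AML and ALL". Section 3.1.2.2 describes the part as run "in 2 separate cohorts of subjects with relapsed or refractory AML and ALL", and section 11.10 plans the size by disease: "Approximately 20 subjects each with AML and ALL will be enrolled at the RDE dose level".

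For safety, section 11.6 states: "Frequency tables of subjects reporting TEAEs will be provided by the worst NCI-CTCAE grade, SOC, preferred term (PT), and by dose level". SAEs and treatment-related TEAEs follow the same pattern. DLTs, laboratory values, histamine, ECG, vital signs, physical examination and ECOG-PS are also by dose level. Section 11.1.2 summarises the Safety Analysis Set by dose received and names four groups: "1) subjects in the Dose Escalation part, (2) subjects in the Dose Expansion part, (3) subjects treated at the dose level of RDE", and fourth, all subjects. None is defined by disease.

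For efficacy, section 11.4 ends its endpoint list with "30- and 60-day mortality rate for AML and ALL, respectively".

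Disease enters safety as a rule of conduct. Under section 3.1.2.2 the first four subjects of each disease are reviewed before that cohort continues. Under section 3.1.8, "the safety will be assessed continuously after 4 subjects are enrolled in each cohort of AML and ALL". Section 9.3 names differentiation syndrome as the adverse event of special interest and says that "it has been reported in 1 subject with AML"; section 11.6 gives it no table of its own.

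**The concern.** Only one regimen goes from Part 1 into Part 2 (sections 3.1.2.1 and 3.1.8), so in Part 2 a table by dose level has essentially one column. That column mixes two diseases which the design otherwise keeps apart. The secondary endpoints are split by disease and the primary one is not.

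If the toxicity profiles differ, the pooled percentage is too low for one disease and too high for the other. Anyone weighing benefit against risk in AML would set an AML response rate beside a safety rate that comes half from ALL subjects, and the reverse.

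**Working it through.** **Inputs.** 20 AML and 20 ALL subjects at the RDE, 40 in total, of whom 6 to 9 may come from Part 1 (section 11.10). All event counts and toxicity rates below are illustrative; the documents give none for Part 2.

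**The plan's own figure.** Section 11.10 supports 20 per disease with the chance of at least 3 CRc at a true rate of 20%:

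1 - [0.8^20 + 20(0.2)(0.8^19) + 190(0.2^2)(0.8^18)] = 1 - (0.0115 + 0.0576 + 0.1369) = 0.794.

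This reproduces the stated 79.4%. It is an efficacy figure; for safety the section gives only the total of 40.

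**Dilution factor.** Let the affected disease have x events in n1 subjects and the other y events in n2. Then

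factor = (x/n1) / [(x + y)/(n1 + n2)].

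With y = 0 this reduces to (n1 + n2)/n1.

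- Planned sizes, y = 0: 40/20 = 2.0.
- Equal cohorts, other disease also affected: at 40% versus 5% the pooled rate is 22.5% and the factor 40/22.5 = 1.78; at 40% versus 10%, 40/25 = 1.60; at 40% versus 20%, 40/30 = 1.33.
- Unequal cohorts of 18 and 22, y = 0: 40/18 = 2.22 for the smaller and 40/22 = 1.82 for the larger.
- RDE column if the 6 to 9 Part 1 subjects come on top of 40 (section 3.1.2.2 can be read that way), y = 0: 46/20 = 2.30 to 49/20 = 2.45 if none has the affected disease; 46/26 = 1.77 to 49/29 = 1.69 if all do.
- If they are counted within the 40, as section 11.10 says, the Dose Expansion column holds 40 - 9 = 31 to 40 - 6 = 34 subjects. The factor is still 2.0 if these split equally and y = 0.

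**Example with exact (Clopper-Pearson) 95% intervals**, limits Beta(0.025; x, n - x + 1) and Beta(0.975; x + 1, n - x):

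| Column | Events | Rate | 95% CI |
|---|---|---|---|
| AML | 4/20 | 20% | 5.7-43.7% |
| ALL | 0/20 | 0% | 0-16.8% |
| Pooled, as planned | 4/40 | 10% | 2.8-23.7% |

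The pooled 10% describes neither cohort.

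**The case against.** Several points on the other side stand.

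- **The information is not lost.** Section 11.6.1 provides a by-subject adverse event listing and lists deaths, other SAEs and events leading to permanent discontinuation. Early mortality is already reported by disease. A reader might infer that the final analysis cannot show tolerability in each disease; that goes too far. Section 11.6.1 does not name diagnosis as a listing item, but its list is open, and with about 40 subjects the split could be rebuilt. Rebuilding rates by hand is still a poor substitute for a planned table on a primary objective.
- **A later SAP may add the split.** Section 11.2 promises a detailed SAP before database lock, and its text is not available here. Sections 11.6.2 to 11.6.4 and 11.6.6.2 also name no grouping for some tables. So the protocol omits the split; it does not forbid it.
- **Pooling has a rationale.** One MTD comes from a mixed Part 1, and section 11.10 rests safety on the total of 40. For a 5% event the chance of at least one case is 1 - 0.95^40 = 87% in 40 subjects and 1 - 0.95^20 = 64% in 20. This is a reason to keep the total column, not to omit the disease columns.
- **The 30% rule of section 3.1.8 is not a yardstick here.** A reader might infer that a pooled column could look safely below 30% while one cohort has reached it. The documents do not support that comparison. The rule is a running conduct rule for clinically relevant toxicities, with listed exceptions and a separate judgement on myelosuppression, and the incidence must exceed 30%. Final Grade 3 or higher TEAE percentages are on a different scale. Whether the rule applies per cohort or pooled is not stated, and is a separate question.
- **Differentiation syndrome is thin evidence.** One AML case among the 22 AML/ALL subjects in section 1.1.1.6 does not show that it is confined to AML, and sections 1.4.2 and 9.3 describe the risk for acute leukemia generally. It is a reason to look by disease, no more.

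**Conclusion.** The point holds as a gap in planned reporting. As written, sections 11.1.2 and 11.6 pool AML and ALL in the Part 2 and RDE safety summaries, while the objective, the cohorts and the efficacy analysis are by disease. A toxicity confined to one disease would be tabulated at about half its rate.

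The factor of 2.0 rests on two assumptions together, equal cohorts and no events in the other disease. It is not a ceiling: the cases worked above run from 1.33 to 2.45. It also assumes that Part 2 subjects are tabulated at one dose level; a de-escalation under section 3.1.2.2 would change the columns.

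Pooling affects the percentages, not the event counts, and monitoring is untouched. The documents contain no contradiction here, and no decision rule reads off these final tables. The change is still worth making before database lock, because it concerns how the primary objective will be read.

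**What to change.** In sections 11.1.2 and 11.6, or in the SAP that section 11.2 promises, present the Dose Expansion group and the RDE group in three columns: AML, ALL and total. Apply this to TEAEs by worst grade, SAEs, treatment-related TEAEs and adverse events leading to discontinuation. Add a by-disease row for differentiation syndrome. Keep the by-dose tables for Part 1.

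This needs extra columns from data already collected and no change of conduct. The downside is smaller cells and wider intervals per disease, as the example shows; the retained total column preserves the precision of the pooled summary.

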#### **11.6.1. Adverse Event Analyses**

A TEAE is defined as an AE that emerges during the treatment period, having been absent at pre-treatment; or reemerges during treatment, having been present at baseline but stopped prior to treatment; or worsens in severity after starting treatment relative to the pre-treatment state, when the AE is continuous.

The number and percentage of subjects reporting TEAEs will be tabulated by the worst NCI-CTCAE grade, SOC, PT, and by dose level.

Similarly, the number and percentage of subjects reporting treatment-emergent SAEs will be tabulated, as well as TEAEs/SAEs considered related to DS-3201b.

A by-subject AE (including TEAE) data listing will be provided including, but not limited to, verbatim term, PT, SOC, NCI-CTCAE grade, and relationship to study drug.

Deaths, other SAEs, and other significant AEs, including those leading to permanent discontinuation from DS-3201b, will be listed.

#### **11.6.2. Clinical Laboratory Evaluation Analyses**

Descriptive statistics will be provided for selected clinical laboratory test results (ie, hematology [including coagulation] and blood chemistry) and changes from baseline by scheduled time of evaluation including the EOT visit, maximum post-treatment value, and minimum post-treatment value.

Abnormal clinical laboratory results will be graded according to NCI-CTCAE, Version 4, if applicable. A shift table, presenting the 2-way frequency tabulation for baseline and the worst post-treatment value according to the NCI-CTCAE grade, will be provided for selected clinical laboratory tests. Abnormal clinical laboratory test results that are deemed of clinical significance or of Grade 3 or 4 will be listed.

#### **11.6.3. Vital Signs Analyses**

Descriptive statistics will be provided for the vital signs measurements and changes from baseline by scheduled time of evaluation, including the EOT visit, and the maximum and minimum post-baseline values.

#### **11.6.4. Electrocardiogram Analyses**

Electrocardiogram parameters (PR, RR, QRS, QT intervals, and corrected QT interval using Bazett's [QTcB], and Fridericia's [QTcF] formulas) will be summarized using descriptive

statistics for actual values and for changes from baseline by scheduled time of evaluation, including the EOT visit and the maximum post-baseline value. The corrected QT intervals using Bazett's and Fridericia's formula will be calculated as follows:

$$QT_{cB} = QT/(RR)^{1/2} \text{ and } QT_{cF} = QT/(RR)^{1/3}$$

The number and percentage of subjects with maximum absolute QT, QTcF, and QTcB intervals meeting pre-defined categories (>450 ms, >480 ms, and >500 ms) over all post-treatment evaluations, as well as in QT, QTcF, and QTcB maximum changes from baseline (>30 ms and >60 ms) over all post-treatment evaluations will be tabulated. A listing of ECG data will be provided.

